# 1.3 Rationale

Phase I studies conducted in healthy Japanese subjects living in Japan indicated an approximate 2-fold increase in rosuvastatin  $C_{max}$  and  $AUC_{(0-24)}$  compared to similar studies conducted in western Caucasian subjects and that the absolute bioavailability in Japanese subjects in Japan was 29% compared to 20% in Caucasians. The population pharmacokinetic

analysis that incorporated race as a categorical variable also demonstrated an approximate 2fold increase in rosuvastatin plasma concentrations in Asian subjects, most of whom were Japanese subjects residing in Japan.

Preliminary results of an ongoing trial in Singapore suggest that systemic exposure in Chinese, Malay, and Indian subjects is higher than in a group of Caucasian subjects. The magnitude of difference between Chinese and Caucasian subjects is similar to that observed between Japanese and Caucasian subjects.

The mechanism for the apparent difference in the pharmacokinetic profile of rosuvastatin between these ethnic groups is unknown. Extrinsic (diet, environment, etc.) and/or intrinsic (genetic) factors could be responsible for these differences.

Plasma exposure of rosuvastatin has not been determined in Asian populations residing in the United States. This study will assess and summarize the pharmacokinetics of a single dose of 20 mg rosuvastatin in Chinese, Filipino, Asian-Indian, Korean, Vietnamese, and Japanese subjects residing in the United States. The study population represents the most populous Asian groups residing in the United States as described in the 2000 United States census report (Barnes, Jessica; Bennett, Claudette; U.S. Census Bureau; Census 2000 Brief; "The Asian Population;" issued February 2002, http://www.census.gov/prod/2002pubs/c2kbr01-16.pdf). Results will be related to pharmacokinetic data obtained from a Caucasian control group to determine if similar differences in exposure occur between these groups.

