# 2. STUDY OBJECTIVES

# 2.1 Primary objective

The primary objective of this study is to summarize rosuvastatin plasma exposure in healthy subjects of Asian heritage who are living in the United States following a single 20 mg dose by measuring  $C_{max}$  and AUC of rosuvastatin and to relate those results to pharmacokinetic data obtained from a Caucasian control group.

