# 6.2 Description of outcome variables in relation to hypotheses

Although there are no hypotheses to be addressed in this protocol, this section will list the outcome variables related to the objectives.

**Rosuvastatin exposure (primary objective):** After a single oral dose of rosuvastatin,  $C_{max}$  and AUC will be determined for each subject. If AUC data cannot be determined in all subjects completing the study, AUC(0-t) will replace AUC as a primary endpoint.

**Rosuvastatin exposure (secondary objective):** The following pharmacokinetic parameters will be estimated and summarized:  $AUC_{(0-t)}$ ,  $t_{1/2\lambda z}$ ,  $t_{max}$ , and CL/F. With exception to CL/F, these pharmacokinetic parameters, along with  $C_{max}$  and AUC, will also be estimated and summarized for N-desmethyl rosuvastatin and rosuvastatin lactone.

**Safety and tolerability (secondary objective):** Incidence and severity of adverse events, blood pressure/heart rate (sitting), laboratory parameters (hematology, clinical chemistry, urinalysis), and physical examination.

**Pharmacogenetic objective:** Genes of interest include OATP-C and MRP-2, and may include any other gene that may be involved with the ADME of statins. Genetic information will not be included in the SAP or study report.

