# 6.3 Description of analysis sets

There are two populations in this study. All subjects receiving the dose of study drug will be included in the safety population. The per-protocol (PP) population, also known as the evaluable population, is defined as a subset of the safety population, excluding those subjects with a protocol deviation felt to significantly influence the pharmacokinetics of the drug. In order to be evaluable, subjects must have completed all study procedures from the screening period to the final blood sampling for plasma levels of rosuvastatin. Definitions of all such protocol deviations will be made in the SAP. Examples include, but are not limited to, major changes in the administration of study drug or co-administration of medications expected to affect the pharmacokinetics.

All safety data will be summarized using the safety population (defined as any subject who received the dose of study drug). Pharmacokinetic data will be summarized using the PP population. In the case of the PP and safety populations being identical, only the safety population will be used throughout; this decision will be made at the time of data review and documented in the SAP.

A test for homogeneity of variance in  $C_{max}$  and AUC will be performed for the subjects in the Asian groups. If the test shows no difference and the means appear similar, then the data will be pooled. This data will be related to pharmacokinetic data generated from the subjects in the Caucasian control group.

The distribution of  $C_{max}$ , AUC and AUC(0-t) values for the Caucasian control group and for the Asian subjects residing in the United States will be summarized using descriptive statistics and presented graphically (e.g. box and whisker plots). There will be no statistical comparisons between groups.

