## 6.4.2 Pharmacokinetics

 $C_{max}$  and  $t_{max}$  for each subject will be determined by inspection of the rosuvastatin plasma concentration-time profile. The terminal elimination rate constant ( $\lambda_z$ ) will be calculated by log-linear regression of the terminal portion of the concentration-time profiles where there are sufficient data (a minimum of 3 plasma concentration values in the terminal log-linear phase, spanning an interval of at least 2 half-lives.) Terminal elimination half-life ( $t_{\nu_2\lambda_z}$ ) will be calculated as  $0.693/\lambda_z$ . The AUC(0-t) will be calculated by the linear trapezoidal rule (AUC = AUC(0-t) + Clast/ $\lambda_z$ ). AUC(0-t) will be extrapolated to infinity using  $\lambda_z$  to obtain AUC where there are sufficient data. Following the single dose administration of rosuvastatin, the CL/F will be calculated as Dose/AUC.

Pharmacokinetic data,  $C_{max}$ , AUC(0-t) and AUC, will be summarized for each Asian ethnic group and pooled, if appropriate, using descriptive statistics, including geometric means and coefficient of variation, and listed. In addition, 95% CI for the mean pharmacokinetic parameters will also be presented.

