# 6.5 Determination of sample size

No formal statistical comparisons will be made between the ethnic groups compared to the Caucasians. However, 22 subjects will be sufficient to characterize the pharmacokinetics of rosuvastatin in these populations subsequent to a single 20 mg dose.

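### The primary objective is to relate Asian exposure to the Caucasian control, but the protocol bars statistical comparisons and names no between-group estimate or interval

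*Protocol*

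**What the plan says.** Section 2.1 sets the primary objective in two parts: to summarize Cmax and AUC in Asian subjects living in the United States, "and to relate those results to pharmacokinetic data obtained from a Caucasian control group". Section 1.3 gives the reason. Studies in Japan showed roughly 2-fold higher exposure than in Caucasian subjects, and the present results will be set beside a Caucasian control group "to determine if similar differences in exposure occur between these groups". Section 3.2 says the control group was included so that its data can be related to the Asian data.

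The statistical sections are descriptive. Section 6.2 opens with "Although there are no hypotheses to be addressed in this protocol". Section 6.3 plans descriptive statistics and plots for the control and the Asian subjects, with conditional pooling of the Asian groups, after which the data are to be related to the control. It closes with "There will be no statistical comparisons between groups". Section 6.4.2 and the synopsis plan geometric means and coefficients of variation, and "In addition, 95% CI for the mean pharmacokinetic parameters will also be presented". Section 6.5 adds "No formal statistical comparisons will be made between the ethnic groups compared to the Caucasians". No section names a ratio, a difference or an interval between groups.

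**The concern.** The objective and the rationale ask how exposure in one group stands to exposure in another. The quantity that answers this for Cmax and AUC is the geometric mean ratio to the control, with its confidence interval. The protocol requires the relating but does not say what will be estimated, and Section 6.3 appears to close the door on the interval.

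At stake is whether the report can say how precisely the difference is known. About 26 healthy controls are recruited, dosed and sampled 19 times each so that the comparison can be made within one study. If only single-group intervals are printed, a reader who wants the comparison may fall back on whether those intervals overlap. That is a stricter criterion than the interval for the ratio itself. Having no hypothesis test is a legitimate choice in a Phase I study, but it does not require giving up the estimate.

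**Working it through.** **The plan's own figures.** Six Asian groups of 22 give 6 × 22 = 132 evaluable, and 6 × 26 = 156 recruited; both match Section 3.1. The figure of 22 per group comes with no CV, precision target, alpha or power, so it cannot be re-derived.

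**Inputs.** n = 22 evaluable per group (Sections 3.1, 3.3.5.2 and 6.5); a ratio of about 2 as the background value (Section 1.3). The between-subject CV is an assumption, because the protocol gives none; 30% to 70% is used as the range, with 80% as a further check.

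**Formulas, on the log scale.**
- σ = √ln(1 + CV²)
- Single-group 95% CI factor: exp(t(0.975, 21) × σ / √22)
- Ratio at which two separate CIs of equal width stop overlapping: the square of that factor
- 95% CI factor for a ratio of two groups: exp(t(0.975, df) × σ × √(1/22 + 1/22)), with df = 42 from the two groups alone, or df = 154 − 7 = 147 from one model over all seven groups

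**CV 50% in full.** σ = √ln(1.25) = 0.472.
- Single-group factor: exp(2.080 × 0.472 / 4.690) = 1.233. Separate CIs stop overlapping at 1.233² = 1.52.
- Ratio factor, 42 df: exp(2.018 × 0.472 × 0.3015) = 1.333. An observed ratio of 2.0 has a CI of 1.50 to 2.67.
- Ratio factor, 147 df: exp(1.976 × 0.472 × 0.3015) = 1.325. An observed ratio of 2.0 has a CI of 1.51 to 2.65.

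**Over the assumed range.**

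| CV | Separate CIs stop overlapping at | Ratio factor, 147 df | Ratio factor, 42 df | CI at observed 2.0 (42 df) |
|---|---|---|---|---|
| 30% | 1.30 | 1.19 | 1.20 | 1.67 to 2.39 |
| 50% | 1.52 | 1.33 | 1.33 | 1.50 to 2.67 |
| 70% | 1.75 | 1.46 | 1.47 | 1.36 to 2.94 |
| 80% | 1.87 | 1.52 | 1.53 | 1.30 to 3.07 |

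If the Asian groups are pooled (132 against 22, 152 df), the ratio factor is 1.14, 1.24, 1.33 and 1.38 for the same four CVs.

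**Reading.** The planned size gives a usable interval for the ratio, so sample size is no reason to omit it. At CV 50%, the direct interval excludes 1 from an observed ratio of about 1.33, while the separate intervals part only at about 1.52. In that band, overlap would suggest no clear difference where the direct interval shows one. For a ratio near 2, the separate intervals do not overlap at any CV in the table.

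**The case against.** The protocol openly declares itself descriptive: the first verb of the objective is to summarize, no hypothesis is stated, and there is no test, alpha or power claim to fail. Sections 6.3 and 6.5 can be read as barring only inferential testing, since Section 6.5 speaks of formal comparisons and Section 6.4.1 of hypothesis tests. Details of the summaries and of data presentation are left to the SAP (synopsis, Section 6.7), which is not at hand.

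Much of this stands, and it limits what can be claimed. A reader might infer that the protocol rules out any between-group estimate and leaves only seven separate summaries with no interval. The documents do not support that:
- A bare ratio of geometric means is unspecified rather than forbidden, and it follows by one division from the planned outputs.
- A pooled Asian summary is also foreseen.
- Within-group intervals are planned; only the between-group one is missing.
- No section prescribes reading overlap of intervals, so the overlap calculation describes a likely misreading and not a rule of the plan. It hardly matters at the 2-fold ratio that prompted the study.

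What does not stand is full deferral to the SAP. The sentence in Section 6.3 is an affirmative bar. On an ordinary reading, a model-based ratio with a confidence interval is a statistical comparison, so an SAP that added one would conflict with the protocol.

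**Conclusion.** The concern holds as a mismatch between the objective and the analysis. The relating clause of the primary objective has no estimator and no stated precision, and the protocol's own wording obstructs supplying them. The point ratio is recoverable from the planned summaries; its uncertainty would not be reported.

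The size rests on 22 evaluable subjects per group, log-normal data, a common variance in the two groups compared, and assumed CVs of 30% to 70%. On those terms the ratio is known to within a factor of about 1.19 to 1.47, and reliance on overlap would mislead mainly for ratios of about 1.33 to 1.52 at CV 50%.

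This is a should-fix. No data, endpoint or sample size is affected, and an approximate interval could be rebuilt from the geometric means, CVs and group sizes.

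**What to change.** Replace the closing sentence of Section 6.3, and align the statistical methods in the synopsis and Sections 6.4.2 and 6.5, along these lines:

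*No hypothesis tests between Asian and Caucasian subjects will be done. For Cmax and AUC (or AUC(0-t), if it replaces AUC), the geometric mean ratio of each Asian group to the Caucasian group, and of the pooled Asian group if one is formed, will be presented with its 95% confidence interval from a model on the log scale, for estimation only.*

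The model should allow unequal variances if needed, because the homogeneity check in Section 6.3 covers only the Asian groups and not the control. State also that the single-group intervals are computed on the log scale and back-transformed, so that they belong to the geometric means.

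The cost is a few sentences and one standard model, with no extra subjects or samples. The downside is a set of unadjusted intervals: 6 groups × 2 parameters = 12, plus 2 if the Asian groups are pooled. They should be labelled as descriptive.

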# 6.4 Methods of statistical analyses

Statistical summaries will be carried out by the biostatistical group at AstraZeneca using the SAS system Version 8. Pharmacokinetic analysis will be carried out by the Clinical Pharmacokinetic Section, Experimental Medicine, at AstraZeneca.

Where standard summary statistics are referenced below, this will include the mean, standard deviation, median, minimum and maximum for continuous variables, and counts and percentages for discrete variables.

## 6.4.1 Demographic and baseline data

All demographic and baseline data, including medications, will be listed and summarized using standard summary statistics. No hypothesis test comparing the Asian subjects with the Caucasian control group will be made. Demographic data from the control group will be summarized as well.

## 6.4.2 Pharmacokinetics

 $C_{max}$  and  $t_{max}$  for each subject will be determined by inspection of the rosuvastatin plasma concentration-time profile. The terminal elimination rate constant ( $\lambda_z$ ) will be calculated by log-linear regression of the terminal portion of the concentration-time profiles where there are sufficient data (a minimum of 3 plasma concentration values in the terminal log-linear phase, spanning an interval of at least 2 half-lives.) Terminal elimination half-life ( $t_{\nu_2\lambda_z}$ ) will be calculated as  $0.693/\lambda_z$ . The AUC(0-t) will be calculated by the linear trapezoidal rule (AUC = AUC(0-t) + Clast/ $\lambda_z$ ). AUC(0-t) will be extrapolated to infinity using  $\lambda_z$  to obtain AUC where there are sufficient data. Following the single dose administration of rosuvastatin, the CL/F will be calculated as Dose/AUC.

Pharmacokinetic data,  $C_{max}$ , AUC(0-t) and AUC, will be summarized for each Asian ethnic group and pooled, if appropriate, using descriptive statistics, including geometric means and coefficient of variation, and listed. In addition, 95% CI for the mean pharmacokinetic parameters will also be presented.

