# 1.2 Clinical pharmacology

In clinical pharmacology studies in man, peak plasma concentrations of rosuvastatin are reached 3 to 5 hours following oral dosing. Both  $C_{max}$  and AUC increase in approximate proportion to rosuvastatin dose. The absolute bioavailability of rosuvastatin in Caucasian subjects is approximately 20%.

Administration of rosuvastatin with food decreased the rate of drug absorption by 20% as assessed by  $C_{max}$  but there was no effect on the extent of absorption as assessed by AUC. Plasma concentrations of rosuvastatin do not differ following evening or morning drug administration. Significant LDL-C reductions are seen when rosuvastatin is given with or without food, and regardless of the time of day of drug administration.

Mean volume of distribution at steady state of rosuvastatin is approximately 134 liters. Rosuvastatin is 88% bound to plasma proteins, mostly albumin. This binding is reversible and independent of plasma concentrations.

Rosuvastatin is not extensively metabolized; approximately 10% of a radiolabeled dose is recovered as metabolite. The major metabolite is N-desmethyl rosuvastatin, which is formed principally by cytochrome P450 2C9, and *in vitro* studies have demonstrated that N-desmethyl rosuvastatin has approximately one-sixth to one-half the 3-hydroxy-3-methlglutaryl coenzyme A (HMG-CoA) reductase inhibitory activity of rosuvastatin. Overall, greater than 90% of plasma HMG-CoA reductase inhibitory activity is accounted for by rosuvastatin.

Following oral administration, rosuvastatin and its metabolites are primarily excreted in the feces (90%). The  $t_{\frac{1}{2}\lambda z}$  of rosuvastatin is approximately 19 hours.

After an intravenous dose, approximately 28% of total body clearance was via the renal route, and 72% by the hepatic route.

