# 3. STUDY PLAN AND PROCEDURES

# **3.1** Overall study design

This is a single-center, open label, single dose, pharmacokinetic study of subjects having Chinese, Filipino, Asian-Indian, Korean, Vietnamese, and Japanese heritage and are residing in the United States. Approximately156 subjects will be recruited with a minimum of 22 subjects and a maximum of 26 subjects from each ethnic group to obtain at least 132 evaluable subjects. Approximately 26 healthy Caucasian subjects will be recruited to obtain at least 22 evaluable subjects. These subjects will serve as a control group for the study.

Rosuvastatin exposure following a single oral dose of 20 mg will be determined by measuring  $C_{max}$  and AUC. In addition,  $AUC_{(0-t)}$ ,  $t_{1/2\lambda Z}$ ,  $t_{max}$ , and CL/F of rousuvastatin and  $C_{max}$ , AUC,  $AUC_{(0-t)}$ ,  $t_{1/2\lambda Z}$ , and  $t_{max}$ , of N-desmethyl rosuvastatin and rosuvastatin lactone will be measured.

Subjects satisfying the inclusion and exclusion criteria and screening exams will enter the clinical research center (CRC) on Day -1. On Day 1 subjects will receive a single dose of rosuvastatin 20 mg under fasting conditions. Blood samples will be taken pre-dose (within 30 minutes) and 0.5, 1, 2, 3, 4, 5, 6, 8, 10, 12, 18, 24, 30, 36, 48, 54, 60, and 72 hours post-dose. After completion of the final blood sample and all safety assessments on Day 4, the subjects will be discharged.

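### Requiring the terminal points to span two half-lives caps the half-life that a 72-hour profile can report, so the half-life summary is truncated by its own value and AUC and CL/F go missing with it

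*Protocol*

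**What the plan says.** Section 6.4.2, repeated in the Synopsis under Statistical Methods, estimates the terminal rate constant by log-linear regression where data are sufficient, and defines sufficient as "a minimum of 3 plasma concentration values in the terminal log-linear phase, spanning an interval of at least 2 half-lives". Three parameters depend on that constant:

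- Half-life is 0.693 divided by it.
- AUC(0-t) is extrapolated with it "to obtain AUC where there are sufficient data".
- For clearance, "the CL/F will be calculated as Dose/AUC".

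Section 3.1 places the post-dose samples at "0.5, 1, 2, 3, 4, 5, 6, 8, 10, 12, 18, 24, 30, 36, 48, 54, 60, and 72 hours post-dose". Section 1.2 says that the terminal half-life "of rosuvastatin is approximately 19 hours" and that "peak plasma concentrations of rosuvastatin are reached 3 to 5 hours following oral dosing".

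Section 6.2 (and Outcome variables in the Synopsis) contains one safeguard: "If AUC data cannot be determined in all subjects completing the study", AUC(0-t) takes the place of AUC as a primary endpoint. Section 6.4.2 still summarises AUC next to AUC(0-t). Half-life and CL/F are secondary parameters in section 2.2, with no substitute named.

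**The concern.** As written, the span is a condition for calculating the rate constant and not a comment on its quality. In a profile of fixed length, such a condition puts an upper limit on the half-life that can be reported. A subject fails because the half-life is long, so the missing values are missing because of their own size. The half-life summary is then cut off from above. AUC and CL/F are lost in the same subjects, so their summaries describe a selected subset. The degree of selection could differ between ethnic groups if half-life differs between them.

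**Working it through.** **Plan's own figure.** The protocol states no expected number of failures, so there is nothing to reproduce.

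**Inputs from the protocol.** Last sample 72 h and the sampling grid (section 3.1); half-life about 19 h and peak at 3 to 5 h (section 1.2); at least 22 evaluable subjects per group (section 3.3.5.2), so 7 × 22 = 154.

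**Assumptions, not in the protocol.** Half-life is lognormal with geometric mean 19 h and between-subject CV 20% to 40%. The terminal phase starts between 12 and 36 h. The 72 h sample is quantifiable.

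**Step 1: the ceiling.** Largest reportable half-life = (last time − start of fit)/2. From a 24 h start this is (72 − 24)/2 = 24 h. Even a fit starting at a 5 h peak gives only (72 − 5)/2 = 33.5 h. A 19 h half-life needs 2 × 19 = 38 h, so the fit must start by 72 − 38 = 34 h, which on the grid means the 30 h sample.

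**Step 2: share failing and bias in half-life.** With s = √ln(1 + CV²) and z = ln(ceiling/19)/s, the share failing is 1 − Φ(z). The geometric mean among those who pass is 19·exp(−s·φ(z)/Φ(z)). For CV 30% and a 24 h ceiling: s = √ln 1.09 = 0.294; z = ln(24/19)/0.294 = 0.80; share failing 21.3%; geometric mean 17.0 h, which is 10.3% low.

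| Start (h) | Ceiling (h) | Failing at CV 20 / 30 / 40% | Geometric mean half-life among passers, h (bias) at CV 20 / 30 / 40% |
|---|---|---|---|
| 12 | 30 | 1.1 / 6.0 / 11.8% | 18.9 (−0.6%) / 18.3 (−3.6%) / 17.4 (−8.3%) |
| 18 | 27 | 3.8 / 11.6 / 18.1% | 18.7 (−1.7%) / 17.8 (−6.3%) / 16.8 (−11.6%) |
| 24 | 24 | 11.9 / 21.3 / 27.2% | 18.2 (−4.4%) / 17.0 (−10.3%) / 15.9 (−16.1%) |
| 30 | 21 | 30.7 / 36.7 / 39.8% | 17.2 (−9.5%) / 16.0 (−16.0%) / 14.8 (−21.9%) |
| 36 | 18 | 60.8 / 57.3 / 55.6% | 15.7 (−17.6%) / 14.5 (−23.6%) / 13.5 (−29.0%) |

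The 36 h row is an extreme, because the typical 19 h subject could not pass. The range quoted in the conclusion uses starts of 12 to 30 h.

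**Step 3: AUC and CL/F.** If log half-life and log AUC have correlation ρ and AUC has an assumed CV of 50%, the geometric mean AUC among passers changes by exp(−ρ·√ln 1.25·φ(z)/Φ(z)) − 1. For a 24 h start and half-life CV 30% this is 0% at ρ = 0, −5% at 0.3, −8% at 0.5 and −12% at 0.7, and CL/F moves the opposite way. Low concentrations can act in the other direction. A subject last quantifiable at 60 h, fitted from 24 h, has a ceiling of (60 − 24)/2 = 18 h, and losing such subjects would raise the AUC summary. The protocol gives neither ρ nor an assay limit, so the net sign is open.

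**Step 4: the switch to AUC(0-t).** Read literally, one failure among the completers triggers it. The chance is 1 − (1 − share failing)^154. It is about 80% in the mildest scenario in the table (CV 20%, 12 h start) and above 99% in every other.

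**Step 5: difference between groups (illustration only).** With a 24 h ceiling and CV 30%, a group with typical half-life 22 h would fail in 38% of subjects, against 21% at 19 h.

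**The case against.** The strongest reply is that the primary comparison does not depend on this rule. Cmax needs no rate constant. If AUC is missing in any completer, AUC(0-t), which needs none either, takes over. This stands. A reader might infer that the primary relation of Asian to Caucasian exposure is drawn from a selected subset. Sections 6.2 and 6.4.2 do not support that, because AUC(0-t) is summarised in any case and becomes primary when AUC is incomplete.

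A reader might also infer that AUC and CL/F are biased in a known direction, or that the group with higher exposure loses more subjects. The protocol does not support this either. Section 1.3 reports absolute bioavailability of 29% in Japanese subjects in Japan and 20% in Caucasians. Higher bioavailability raises AUC without lengthening half-life, so higher exposure need not mean more failures.

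A minimum span is also a legitimate precision criterion, since a slope fitted over a short interval is unreliable. That is a reason to mark such values. It does not remove the truncation that follows from omitting them. Replacing the rule by a limit on the extrapolated share would be no cure. In a one-compartment approximation the share beyond 72 h is 2^(−72/half-life), about 7% at 19 h and 20% at about 31 h, so a 20% limit is a higher ceiling of the same kind.

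Finally, the study tests no hypotheses, and handling of values that cannot be estimated is usually left to the SAP, which is not at hand. Both points limit the weight of the concern. The objection here is to a rule that the protocol itself fixes, in two places.

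**Conclusion.** The concern holds for half-life, and conditionally for AUC and CL/F. Downward bias in the half-life summary is certain once any subject exceeds the ceiling. Its size is not determined by the protocol: for a lognormal half-life around 19 h, CV 20% to 40% and terminal-phase starts of 12 to 30 h, about 1% to 40% of subjects fail and the geometric mean is about 0.6% to 22% too low. AUC and CL/F will be summarised in a selected subset, but whether and in which direction that biases them depends on a relation between half-life and exposure that is not given. The primary exposure summary is largely protected, although the rule makes the move from AUC to AUC(0-t) very likely. Half-life and CL/F have no fallback. The consequence is therefore for secondary descriptive parameters and for AUC as a supporting summary.

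**What to change.** In the Synopsis (Statistical Methods) and section 6.4.2, turn the two-half-life span from a condition for calculation into a reliability flag:

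- Calculate the rate constant, half-life, AUC and CL/F wherever at least three terminal log-linear points exist, and flag values that miss the span.
- Report, per ethnic group, the number flagged and the extrapolated share of AUC.
- Present the summaries with and without flagged subjects, beside AUC(0-t) in all subjects.

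This costs two wording changes and one additional set of summaries, with no extra samples or subjects. The drawback is that flagged values are less precise, which the paired summaries make visible.
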